2.6 PATIENT-REPORTED OUTCOMES OBJECTIVES

Refer to Section [2.1.2](#) for patient-reported secondary efficacy objectives.

The additional patient-reported outcome (PRO) objective of the study is to assess treatment impact and disease symptoms from the sub-scales of the EORTC QLQ-C30 that assess diarrhea, constipation, lack of appetite, fatigue, and two additional items from the EORTC item bank that assess bloating and abdominal pain associated with cobimetinib plus atezolizumab compared with regorafenib in patients with mCRC.

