6.5 PATIENT-REPORTED OUTCOMES ANALYSES

For PROs, the EORTC QLQ-C30 questionnaire and two additional items will be scored according to the EORTC Scoring Manual.

The primary analysis population for evaluation of PRO assessments will include patients in the ITT population with a baseline PRO assessment and at least one post-baseline PRO assessment.

Data from the physical function scale and the global health status/quality of life will be analyzed as a time to deterioration, which will be compared as secondary efficacy endpoints among treatment groups with use of the log rank test (2-sided). Deterioration will be defined as 1) a decrease of 10 points on a transformed 0 to 100 score from baseline on the physical function score or the global status/quality of life scores, or 2) death, or 3) progression. The HR will be estimated using a stratified Cox proportional hazards model and its 95% CI will be provided.

For each assessment timepoint and for each treatment arm, the mean (and 95% CI) and median (and inter-quartile ranges) of the absolute scores for the EORTC QLQ-C30 and additional items and their changes from baseline (Cycle 1 Day 1), will be calculated.

Exploratory descriptive analyses will be conducted using post-treatment data.

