2.2.4 Patient-Reported Outcomes Objectives

The additional patient-reported outcome objective of the study is to assess treatment impact and disease symptoms from the sub-scales of the EORTC QLQ-C30 questionnaire that assess diarrhea, constipation, lack of appetite, fatigue, and two additional items from the EORTC item bank that assess bloating and abdominal pain associated with cobimetinib plus atezolizumab compared with regorafenib in patients with metastatic mCRC.

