4.4.2.4 Patient-Reported Outcomes

Data from the EORTC QLQ-C30 questionnaire and two additional items from the EORTC Item Bank will be scored according to the EORTC scoring manual (Fayers et al. 2001).

The primary analysis population for evaluation of patient-reported outcome (PRO) assessments will include patients in a modified ITT population with a baseline PRO assessment and at least one post-baseline PRO assessment.

Data from the physical function scale and the global health status/quality of life sub-scale of the EORTC QLQ-C30 will be analyzed as time to clinically meaningful deterioration, which will be compared as secondary efficacy endpoints among treatment groups with use of the log rank test (2-sided). Confirmed clinically meaningful deterioration will be defined as a ≥ 10 -point decrease (on a transformed 0 to 100 score) from baseline on the physical function score or the global status/quality of life scores that must be held for at least two consecutive assessments or an initial ≥ 10 -point decrease from baseline followed by death within 4 weeks of the last assessment. Data for patients who do not achieve a 10-point decrease will be censored at the last time PRO data are available. The HR will be estimated using a stratified Cox proportional hazards model and its 95% CI will be provided.

Summary statistics (mean, standard deviation, median, and range) of absolute scores and mean changes from baseline will be calculated for all items and subscales of the EORTC QLQ-C30 and the two additional items from the EORTC Item Bank at each assessment timepoint for each arm while patients are receiving treatment. The mean (and 95% CI) and median of the absolute scores and the changes from baseline to each follow-up point will be reported for categorical and continuous variables, and the proportion of patients selecting each response option will be reported for the two additional items from the EORTC Item Bank. Previously published minimally important

differences (of 10 points) will be used to identify meaningful change from baseline within each treatment group on the functional and disease or treatment-related symptoms scales (Osoba et al. 1998; Cocks et al. 2011). Additional sensitivity analyses may be conducted.

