A longitudinal analysis for the physical functioning and global health status/HRQoL subscales may be conducted to estimate the effect difference on PRO-repeated responses over a selected period of time and between the treatment arms, and mixed models on a set of covariates (baseline domain score, patient demographic, and clinical variables) may be conducted.

In the event of incomplete data, for all questionnaire subscales, if more than 50% of the constituent items are completed, a prorated score will be computed consistent with the scoring manuals and validation papers. For subscales with less than 50% of the items completed at a given timepoint, the subscale will be considered as missing. PRO completion, compliance rates, and reasons for missing data will be summarized at each timepoint by treatment arm.

Exploratory descriptive analyses will be conducted using post-treatment data.

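### The six-symptom PRO objective is comparative (cobimetinib plus atezolizumab against regorafenib), but the SAP plans only within-arm results for those symptoms and no A versus C estimate

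*SAP*

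**What the plan says.** The objective is worded as a comparison. SAP 2.2.4 names four QLQ-C30 symptoms and two item-bank questions and ends with "bloating and abdominal pain associated with cobimetinib plus atezolizumab compared with regorafenib". Protocol 2.6 has the same wording: "bloating and abdominal pain associated with cobimetinib plus atezolizumab compared with regorafenib in patients with mCRC".

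The analysis in SAP 4.4.2.4 has three parts:

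- **Time to deterioration.** This is a between-arm analysis (two-sided log-rank test, stratified Cox HR with 95% CI), limited to physical function and global health status/QoL.
- **Longitudinal model.** This would estimate a difference between arms, but it is optional and introduced for the same two subscales: "A longitudinal analysis for the physical functioning and global health status/HRQoL subscales may be conducted".
- **Summaries of all items and subscales.** Scores and changes from baseline are given "at each assessment timepoint for each arm while patients are receiving treatment", with means, 95% CIs and medians, and response-option proportions for the two added items. A published 10-point difference "will be used to identify meaningful change from baseline within each treatment group on the functional and disease or treatment-related symptoms scales".

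Protocol 6.5 is also by arm: "For each assessment timepoint and for each treatment arm, the mean (and 95% CI) and median". SAP 1 and SAP 4 state that the SAP takes precedence over the protocol's analyses for filing.

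**The concern.** The six symptoms are covered only by the third part, so the plan produces a result for Arm A and a result for Arm C but not the difference that the objective asks about.

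Symptoms can change in every arm because the disease progresses. A before-and-after reading of one arm mixes that shared change with any effect of treatment, and only the contrast between randomised arms separates them. If one arm's change passes 10 points and the other's does not, a reader may take this as a treatment difference when the true changes are equal. The trial is open-label, and the protocol lists diarrhea and fatigue as effects of both cobimetinib (1.5.2) and regorafenib (5.1.3), so tolerability is where such a reading is likely. The randomised data that would answer the question are collected anyway.

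**Working it through.** **Does another section supply the contrast?**

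- SAP 4.4.4, first branch: compares secondary and exploratory endpoints, but between Arms A and B, and only if both OS tests succeed. Regorafenib is not involved.
- SAP 4.4.4, second branch: a descriptive look at atezolizumab's contribution if only A versus C succeeds on OS. It specifies no symptom contrast with regorafenib.
- SAP 4.4.2.4 leaves room for further sensitivity analyses but names no method.
- Elsewhere the SAP does specify between-arm results: a CI for the ORR difference (4.4.2.2), a CI for the difference in OS rates (4.4.3.1), and a descriptive log-rank comparison for DOR (4.4.2.3).

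Nothing fills the gap.

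**How unreliable is a side-by-side reading?** The documents give no power or precision figure for the symptom scales, so there is none to reproduce. The calculation below is an illustration.

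Inputs from the documents: about 180 patients in Arm A and 90 in Arm C; threshold 10 points. Assumed: SD of the change score 20 to 30; 50% to 80% of patients contributing at a visit (n = 90/45 to 144/72); threshold applied to the observed arm mean.

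For a true mean change μ shared by both arms, arm k crosses with probability p_k = 1 − Φ((10 − μ)/SE_k), where SE_k = SD/√n_k. The arms fall on different sides with probability p_A(1 − p_C) + p_C(1 − p_A).

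Most favourable corner, SD 20 and n = 144/72: SE_A = 20/√144 = 1.667; SE_C = 20/√72 = 2.357.
- μ = 8: p_A = 1 − Φ(1.20) = 0.115; p_C = 1 − Φ(0.849) = 0.198. Discordance = 0.115 × 0.802 + 0.198 × 0.885 = 0.27.
- μ = 6: p_A = 0.008; p_C = 0.045. Discordance = 0.05.

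Least favourable corner, SD 30 and n = 90/45: SE_A = 3.162; SE_C = 4.472.
- μ = 8: p_A = 0.264; p_C = 0.327. Discordance = 0.264 × 0.673 + 0.327 × 0.736 = 0.42.
- μ = 6: p_A = 0.103; p_C = 0.186. Discordance = 0.25.

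By symmetry μ = 12 gives the same values as μ = 8. With every patient contributing (180/90), discordance at 8 or 12 points is 23% to 35%, and at 5 points 1% to 7%.

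**What would a direct contrast give?** SE = SD × √(1/n_A + 1/n_C).
- SD 20, n = 144/72: SE = 2.887; 95% CI half-width 1.96 × 2.887 = 5.7 points.
- SD 30, n = 90/45: SE = 5.477; half-width 10.7 points.

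Power for a true 10-point difference (two-sided 0.05) would be 93% and 45% respectively. These figures take no credit for baseline adjustment and make no allowance for selective dropout.

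**The case against.** Four points on the other side have weight.

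1. A reader might infer that the randomised arms are never contrasted on PROs. The documents do not support that: physical function and global health status are compared between arms. The gap is confined to the symptom scales.

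2. A reader might infer that the SAP assigns each arm a yes/no label and compares labels. It does not say so, nor whether the 10 points applies to arm means or to individual patients. Planned outputs include means with 95% CIs, which can reveal a large difference: at SD 20 and n = 144/72, true changes of 25 and 15 give expected intervals of about 21.7 to 28.3 and 10.4 to 19.6. At SD 30 and n = 90/45 they overlap (18.8 to 31.2 and 6.2 to 23.8), and in neither case does the plan report the difference.

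3. It is tempting to quote a 50% discordance rate. That arises only when the shared change sits exactly on the threshold, and it would arise there for any threshold, SD or sample size. Nothing in the documents places the symptom changes at 10 points. The percentages above also count both directions: at a shared change of 8 points, the specific error of regorafenib crossing while the combination does not has probability 0.198 × 0.885 = 18% to 0.327 × 0.736 = 24%.

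4. The objective is an additional one, absent from the secondary efficacy list and outside the alpha hierarchy. Protocol 4.5.10 describes the PRO collection as characterising the combination's clinical profile relative to regorafenib, so description by arm is defensible, if minimal.

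These points limit the size of the concern. They do not remove it: the objective is comparative, and no A versus C result is specified for any of the six symptoms.

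**Conclusion.** The concern holds in limited form. For the six named symptoms, the SAP's within-arm summaries and within-arm 10-point reading do not answer the stated comparison with regorafenib, and no other section does. This follows from the text and needs no assumptions.

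The size of the misreading risk does need them. With SD 20 to 30, 50% to 80% contributing and the threshold applied to arm means, equal true changes would fall on different sides 27% to 42% of the time at 8 or 12 points and 5% to 25% at 6 points. The risk matters mainly when the shared change is near 10 points and is small well below it.

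OS and the secondary efficacy conclusions are untouched. The change is worth making because it is cheap and aligns the analysis with its objective; it does not rescue a failing analysis.

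**What to change.** In SAP 4.4.2.4, for each of the six symptoms in SAP 2.2.4, specify the A minus C difference in change from baseline with 95% CI at the scheduled visits. Both arms complete the questionnaire on Day 1 of 28-day cycles, so visits align. Estimate it from a mixed model with baseline score, arm, time, arm-by-time and the two randomisation strata (extended RAS status; time since first metastasis under or at least 18 months).

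Add four statements to the text:
- The analysis is exploratory and carries no alpha.
- On-treatment data are open to differential discontinuation between arms, so the estimate is not a clean randomised comparison at later visits.
- The within-arm 10-point reading is description only.
- Differing within-arm results are not evidence of a treatment difference.

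Two extensions are best left out. B minus C is not part of this objective, and Arm B's 21-day cycles mostly do not line up with Arm C's 28-day cycles. A 10-point time-to-deterioration rule suits single items poorly: four response categories on a 0 to 100 scale move in steps of 100/3, about 33 points, so any one-category worsening would count as an event.

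Cost: SAP wording and a few tables from data already collected, with no added patients, visits or alpha. The downside is a few extra exploratory estimates without multiplicity control.

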4.4.3 Exploratory Efficacy Endpoints

4.4.3.1 Overall Survival/Progression-Free Survival Rate at Fixed Timepoints

The OS and PFS rates at fixed timepoints (e.g., 6, 12, 18, 24 months) after randomization in ITT populations will be estimated for each treatment arm using Kaplan-Meier methodology, along with 95% CI calculated with the standard error derived from Greenwood's formula. The 95% CI for the difference in OS rates between the two treatment arms will be estimated using the normal approximation method, with standard errors computed by use of Greenwood's method.

4.4.3.2 Time to Response

TTR is defined for patients with an objective response as the time from randomization to the first occurrence of a CR or PR as determined by the investigator using the RECIST v1.1. TTR will be summarized for descriptive purposes. The mean, standard error, median, and range of TTR will be provided. No formal treatment comparisons will be performed.

4.4.3.3 Health Economic Analyses

Health economic data, as assessed by the EQ-5D-5L, will be evaluated for patients with a baseline assessment and at least one post-baseline EQ-5D-5L assessment that generates a score. Scores at baseline and change-from-baseline scores for each timepoint will be quantified using descriptive statistics. Patients without post-baseline assessments will be excluded from this analysis. A single summary index from the

EQ-5D-5L health states will be utilized in this study for economic modeling. These results will not be reported in the Clinical Study Report (CSR).

4.4.4 Evaluation of Each Drug's Contribution to The Combination

If both of the primary comparisons (i.e., Arm A vs. Arm C and Arm B vs. Arm C) for OS are statistically significant, OS as well as other secondary and exploratory endpoints will be compared between experimental arms (i.e., Arm A vs. Arm B) using the same methods described in Sections 4.4.1, 4.4.2, and 4.4.3. The clinical benefit associated with adding cobimetinib to atezolizumab will be evaluated with the focus on clinically meaningful improvement rather than statistical significance.

If the OS comparison for Arm A versus Arm C is statistically significant but the OS comparison for Arm B versus Arm C is not, atezolizumab's contribution to the treatment effect in Arm A will be evaluated for all study endpoints. The evaluation of clinical benefit by adding atezolizumab to the combination will use descriptive statistics (e.g., point estimate and confidence intervals) without hypothesis testing.

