6.4.1 Primary Efficacy Endpoint

The primary efficacy endpoint is OS, which is defined as the time (in months) between the date of randomization and the date of death due to any cause. Patients who have not died at the time of analysis will be censored at the date when they were last known to be alive.

Comparisons with respect to OS between two treatment arms (i.e., Arm A vs. Arm C, Arm B vs. Arm C) will be tested based on a stratified log-rank test. The stratification factors will be extended RAS mutation status of the tumor and time since diagnosis of first metastasis (< 18 months and \geq 18 months).

Each comparison will be tested at a 2-sided significance level of 0.05 within the ITT population:

- Test to reject the null hypothesis of no difference in OS between either experimental arm (i.e., Arm A or Arm B) and the control arm (Arm C) in the ITT population. If the 2-sided p-value corresponding to the stratified log-rank test is less than 0.05, the null hypothesis will be rejected.

The HR for OS will be estimated using a stratified Cox model. Two-sided 95% CIs for the HR will be provided. The stratified analyses will incorporate extended RAS mutation status and time since diagnosis of first metastasis as stratification factors. Results from an unstratified log-rank test and the unstratified HR will also be presented. Kaplan-Meier methodology will be used to estimate median OS for each treatment arm, and the Kaplan-Meier curves will be provided. The Brookmeyer-Crowley methodology will be used to construct the 95% CI for the median OS for each treatment arm ([Brookmeyer and Crowley 1982](#)).

The comparison between the two experimental arms (Arm A vs. Arm B) will be conducted for descriptive purposes.

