Table 2	Operating Characteristics for the Comparison of Arm A versus Arm B with Approximately 165 Overall Survival Events	12

LIST OF FIGURES

Figure 1	Study Schema.....	7
Figure 2	Overview of Hierarchical Testing Sequence for Type 1 Error a Control (2-Sided).....	10

LIST OF APPENDICES

Appendix 1	Protocol Synopsis	22
Appendix 2	Schedule of Assessments.....	33
Appendix 3	Schedule of Pharmacokinetic and Immunogenicity Samples.....	44
Appendix 4	Internal Monitoring Committee Charter	45

1. **BACKGROUND**

This Statistical Analysis Plan (SAP) provides details of the planned analyses and statistical methods for Study GO30182 (IMblaze370): A Phase III, open-label, multicenter, three-arm, randomized study to investigate the efficacy and safety of cobimetinib plus atezolizumab and atezolizumab monotherapy versus regorafenib in patients with previously treated unresectable locally advanced or metastatic colorectal adenocarcinoma. The background for the study can be found in the study protocol.

It is anticipated that positive results from Study GO30182 will support the submission of filing applications globally for the use of cobimetinib plus atezolizumab for the treatment of patients with chemotherapy-refractory, unresectable, locally advanced or metastatic colorectal cancer. For purposes of registration, the analyses outlined in this SAP will supersede those specified in the protocol.

2. **STUDY DESIGN**

This is a Phase III, multicenter, open-label, three-arm, randomized study in patients with unresectable locally advanced or metastatic colorectal cancer (mCRC) who have received at least two prior regimens of cytotoxic chemotherapy for metastatic disease. The study compares regorafenib, a standard-of-care therapy in this setting, with cobimetinib plus atezolizumab and atezolizumab monotherapy.

[figure not shown]
This study will be conducted globally, and approximately 360 patients will be randomized in a 2:1:1 ratio to one of the following treatments:

- Arm A: cobimetinib 60 mg orally on Days 1–21 plus atezolizumab 840 mg intravenous (IV) on Day 1 and Day 15 in a 28-day cycle (n=approximately 180), or
- Arm B: atezolizumab monotherapy 1200 mg IV on Day 1 in a 21-day cycle (n=approximately 90), or
- Arm C: regorafenib 160 mg orally on Days 1–21 in a 28-day cycle (n=approximately 90).

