2.4.2 Analysis Timing for Experimental Arm Comparison

If both of the primary comparisons (i.e., Arm A vs. Arm C and Arm B vs. Arm C) are statistically significant for OS, then OS between the experimental arms (i.e., Arm A vs. Arm B) will be compared at the time of the primary analysis. At this time, a total of approximately 165 OS events are expected from Arms A and B, corresponding to an

MDD in HR of 0.72. The operating characteristics for selected target HRs comparing Arm A with Arm B is presented in [Table 2](#).

Table 2 Operating Characteristics for the Comparison of Arm A versus Arm B with Approximately 165 Overall Survival Events

Target HR	Power	95% CI ^a
0.61	85%	(0.44, 0.84)
0.67	69%	(0.48, 0.93)
0.75	42%	(0.54, 1.04)

FPI= first patient in; HR = hazard ratio; mOS = median overall survival.

^a 95% CI when the target HR is observed.

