4. STATISTICAL METHODS

The analyses described in this SAP will supersede those specified in Protocol GO30182 for the purpose of a regulatory filing.

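### If only A beats C, SAP 4.4.4 plans to estimate atezolizumab's contribution to Arm A with no comparator that could supply it, and does not specify A vs B there

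*SAP*

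**What the plan says.** SAP section 2 sets out the design: "The study compares regorafenib, a standard-of-care therapy in this setting, with cobimetinib plus atezolizumab and atezolizumab monotherapy". Allocation is 2:1:1 to A, B and C, and no arm receives cobimetinib alone.

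SAP 4.4.4 has two branches.

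- **Both primary OS tests significant.** A is compared with B "using the same methods described in Sections 4.4.1, 4.4.2, and 4.4.3". The stated aim is to judge what cobimetinib adds to atezolizumab, with weight on clinical meaning over significance. SAP 2.4.2 sets the same condition: "If both of the primary comparisons (i.e., Arm A vs. Arm C and Arm B vs. Arm C) are statistically significant for OS".
- **A vs C significant, B vs C not.** Atezolizumab's "contribution to the treatment effect in Arm A will be evaluated for all study endpoints". On method: "The evaluation of clinical benefit by adding atezolizumab to the combination will use descriptive statistics", with no hypothesis test. No comparator is named.

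Protocol 6.4.1 and the protocol synopsis attach no condition: "The comparison between the two experimental arms (Arm A vs. Arm B) will be conducted for descriptive purposes". On precedence, SAP section 4 states: "The analyses described in this SAP will supersede those specified in Protocol GO30182 for the purpose of a regulatory filing". SAP section 1 says the same for registration.

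The synopsis in SAP Appendix 1 repeats the protocol's sentence, but it is a copy of the version 4 protocol synopsis and is not separate evidence.

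**The concern.** The benefit of adding atezolizumab to the combination is the effect of A against cobimetinib alone. In the A-only outcome the SAP asks for point estimates and intervals for that effect on every endpoint, and the trial has no arm to subtract. An analyst following the text would produce either nothing or a contrast credited to the wrong drug. In the same outcome the SAP does not specify the one component contrast the trial can estimate.

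What is at stake is interpretation. A significant A vs C beside a non-significant B vs C does not show that A and B differ. Without an A vs B hazard ratio and interval, a reader may conclude that cobimetinib supplied the benefit. SAP section 1 anticipates a filing for the combination, so each component's role will be examined.

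**Working it through.** **1. Which contrast estimates what**

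| Contrast | Randomised here? | Estimates |
|---|---|---|
| A vs C | yes | combination against regorafenib |
| B vs C | yes | atezolizumab against regorafenib |
| A vs B | yes | cobimetinib added to atezolizumab |
| A vs cobimetinib alone | no such arm | atezolizumab added to cobimetinib |

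The second branch of SAP 4.4.4 describes the last row. The only single-agent cobimetinib results in colorectal cancer in the documents are non-randomised: 14 patients, all with progressive disease (Protocol 1.5.2).

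**2. The SAP's own figures**

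The formula is power = Φ(−ln HR × √(d·p·(1−p)) − 1.96), where d is the number of events and p the allocation share.

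- A vs C: 178 events at 2:1, HR 0.61. 0.4943 × √(178 × 2/9) = 3.109, giving 87.5% (stated 87%).
- B vs C: 127 events at 1:1, HR 0.61. 0.4943 × √(127/4) = 2.785, giving 79.5% (stated 80%).
- A vs B: 165 events at 2:1. At HR 0.61, 0.67 and 0.75 this gives 84.9%, 67.9% and 41.4% (stated 85%, 69% and 42%).

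Implied deaths are C = 178 + 127 − 235 = 70, A = 108 and B = 57, so A + B = 165, as stated. The figures reproduce; the point is not a numerical error.

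**3. How often the A-only outcome occurs**

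The two test statistics share Arm C. Their correlation is 1/√((1/2 + 1)(1 + 1)) = 0.577 from the allocation. From the implied deaths it is (1/70)/(√(1/108 + 1/70) × √(1/57 + 1/70)) = 0.52. The table uses a bivariate normal with A vs C at HR 0.61 and both tests two-sided at 0.05.

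| True B vs C HR | Source | Both significant | A only |
|---|---|---|---|
| 0.61 | SAP 2.3 | 73.4-74.0% | 13.5-14.0% |
| 0.80 | assumed | about 24% | about 64% |
| 1.0 | assumed | 3.5-3.7% | about 84% |

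A simulation at the design HRs gave A-only in 15.5-15.7%. It used exponential survival with a control median of 6.4 months, 180/90/90 patients, cutoff at the 235th death, 10% dropout per 24 months, and uniform accrual over 12 or 16 months (the accrual pattern is assumed). A-only becomes likelier than a double success only if the true B vs C HR exceeds about 0.72.

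**4. What A vs B would look like in that outcome**

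At 165 events the 95% interval runs from HR × 0.72 to HR × 1.38, from exp(±1.96/√(165 × 2/9)). At the design HRs the true A vs B HR is 0.61/0.61 = 1.0. A normal approximation with deaths of 108, 57 and 70, keeping only A-only trials, gives a median A vs B HR of about 0.84. About 12% of the 95% intervals exclude 1, against 5% over all trials. The simulation agrees: median 0.84, with the interval including 1 in about 88%. Selecting trials in which B did not win pushes the estimate toward cobimetinib.

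**5. What is and is not missing**

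SAP 4.4.1 ties the OS analysis to the two comparisons with C, and PFS follows the same methods. SAP 4.4.2.2 gives an interval for the ORR difference between arms without limiting it to contrasts with C. Per-arm medians, Kaplan-Meier curves and ORR are reported in any case. The gap is therefore mainly the A vs B hazard ratios for OS and PFS.

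**The case against.** The strongest reply is that nothing is lost. The precedence clause covers analyses the SAP describes. The SAP describes no A vs B analysis for the A-only outcome, so the protocol's unconditional descriptive comparison arguably still stands. This has force. A reader might infer that the SAP cancels A vs B or contradicts the protocol, and the documents do not support that: the SAP is silent for this outcome. But the SAP does specify A vs B, in two places and with a condition, and an analyst should not have to settle precedence after seeing the results.

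A second reply is that the atezolizumab paragraph may be a loosely worded descriptive counterpart to the A vs B paragraph. If so, it names the wrong drug, because A vs B measures cobimetinib's addition. If an external comparison was meant, it is unspecified. Either way the text needs correcting. Forgoing a hypothesis test does not supply a comparator.

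A third reply concerns the remedy: an A vs B estimate read only when B has failed is biased toward cobimetinib. This stands. It would be too strong to say that the hazard ratio simply reveals a true value of 1.0, as step 4 shows. It is a reason to attach a caution; omitting the estimate would leave readers with the less reliable inference from one significant and one non-significant test.

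**Conclusion.** The point holds as a flaw in SAP 4.4.4 and a mismatch in scope with Protocol 6.4.1. In the A-only outcome the SAP plans an estimate that no randomised contrast in this trial can give. It also leaves unstated whether the contrast that isolates a component will be reported. It should be fixed, but it does not touch the primary tests, alpha, event counts or stated power.

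At the design hazard ratios the A-only outcome occurs in about 14-16% of trials. A reader might infer that it is the likely result. That requires a B vs C hazard ratio above about 0.72; the 64% and 84% figures rest on assumed values of 0.80 and 1.0, which are not in the documents. Nor is the ORR difference plainly missing, since SAP 4.4.2.2 does not restrict it.

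The reading of the text does not depend on any calculation. The frequencies rest on proportional hazards and the planned event counts; the simulated ones also rest on the assumed accrual.

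**What to change.** 1. In SAP 2.4.2 and 4.4.4, report A vs B whatever the B vs C result: OS and PFS hazard ratios with 95% CI, and the ORR difference with 95% CI. Label it descriptive and as cobimetinib's added effect, in line with Protocol 6.4.1. Any A vs B log-rank test can stay conditional on both primary tests succeeding.
2. Replace the atezolizumab paragraph of SAP 4.4.4 with a statement that its contribution to Arm A is not estimable from a randomised contrast in this trial. Alternatively, name the external single-agent cobimetinib comparator and state its limits.
3. Add a caution that, read only when A beats C and B does not, the A vs B hazard ratio is selected toward cobimetinib, with the step 4 figures.

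The cost is SAP wording and a few descriptive tables from the same data at the same cutoff. The downside is one more comparison shown without alpha control, subject to that selection when read only in the A-only outcome. The protocol already plans it as descriptive.
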